10.3 Benefits and risks assessment, group relatedness

The study targets a reversible condition (PCDS) with established low-risk interventions. Potential benefits include improved physical/cognitive function, reduced frailty, enhanced neuroplasticity (mBDNF), better quality of life, reduced social isolation, and free nutritional counseling/monitoring for elderly; social-emotional development and healthy lifestyle education for children. Control group receives education and assessments, minimizing inequity.

Risks are minimal: mild physical strain or fatigue from exercise, minor venipuncture discomfort, initial social awkwardness. These are mitigated by screening, supervised progressive interventions, safety monitoring, and termination criteria. The benefit-risk ratio is highly favorable for both groups.

10.4 Compensation and incentives

Participation is voluntary. Elderly participants receive transport reimbursement (Rp 100,000 per orphanage visit if using their own transport) or free shuttle service, plus snacks/drinks (\approx Rp 50,000 value per intergenerational session). Compensation for assessment visits (three time points) covers time/travel. Children receive stationery/books as an appreciation after sessions. No cash incentives are provided to avoid coercion.

10.5 Confidentiality

Participant identity and data confidentiality are strictly protected. Data are coded with unique study IDs; personal identifiers are stored separately in password-protected files accessible only to authorized research team members. Paper records are kept in locked cabinets. Data will be used solely for research purposes; publications/presentations will use aggregated or anonymized data only. No individual data will be shared with third parties without additional consent or ethical approval.

10.6 Insurance and compensation for injury

Although risks are minimal and no serious intervention-related injury is anticipated, the principal investigator maintains professional liability coverage. In the unlikely event of study-related harm, participants will receive appropriate medical care at no cost, coordinated by the research team.

11. ADMINISTRATIVE ASPECTS, MONITORING AND PUBLICATION

11.1 Handling and storage of data and documents

All study data will be handled with strict confidentiality and in compliance with Indonesian regulations on personal data protection.

- Participant identifiers (name, contact details, date of birth) will be linked to a unique study ID in a separate, password-protected master file accessible only to the principal investigator and authorized research team members.
- Case report forms (CRFs) will be completed in paper format initially and stored in locked cabinets at the principal investigator's secure office (School of Medicine and Health Sciences, Atma Jaya Catholic University of Indonesia or affiliated site).
- Data will be double-entered into a password-protected electronic database (SPSS or equivalent) for analysis. Electronic files will be stored on encrypted institutional computers or secure cloud storage with access restricted to the research team.
- Informed consent forms will be stored separately from CRFs in a locked cabinet.
- Audio/video recordings (if any, e.g., tele-exercise sessions) will be deleted after quality checks.

- Biological samples (serum aliquots) will be coded with study ID only and stored at -80°C in an accredited laboratory until analysis; remaining samples will be destroyed after study completion.
- All study documents and data will be retained for at least 15 years post-study completion, after which they will be securely destroyed.

11.2 Monitoring and Quality Assurance

Given the minimal-risk nature of this community-based behavioral intervention study, formal external monitoring is not required. Quality assurance and internal monitoring will be conducted by the principal investigator:

- Regular site visits to community centers and orphanages to verify adherence to protocol, facility preparation, and session conduct.
- Review of attendance logs, session checklists, and adverse event records monthly.
- Inter-rater reliability checks for physical measurements maintained through periodic calibration and co-assessments.
- Data entry accuracy verified by random spot-checks (10% of CRFs).
- Any protocol deviations will be documented and reported to the Ethics Committee if substantial.

11.3 Amendments

Substantial amendments (changes potentially affecting participant safety, rights, or scientific integrity) will be submitted in writing to the approving Ethics Committee for review and approval before implementation. Non-substantial amendments (e.g., minor administrative updates, contact details) will be recorded internally and notified annually or at study close-out.

11.4 Annual progress report

If the study duration exceeds one year, an annual progress report (including enrollment status, adverse events summary, deviations, and preliminary safety data) will be submitted to the Ethics Committee within 60 days of the approval anniversary date.

11.5 End of study report

- Temporary halt for safety or logistical reasons will be notified to the Ethics Committee within 15 days, with reasons and resumption plan.
- The end of the study (defined as the last participant's final assessment) will be notified to the Ethics Committee within 8 weeks.
- A final study report summarizing methods, results, adverse events, and conclusions will be submitted within one year of study completion.

11.6 Public disclosure and publication policy

The study will be conducted with commitment to transparent dissemination of results.

- Results will be published in peer-reviewed scientific journals.
- Authorship will follow International Committee of Medical Journal Editors (ICMJE) guidelines, with principal contributors listed.
- No sponsor or external party has veto rights over publication.
- Aggregated results will be shared with participating community programs and orphanages for feedback and potential implementation.
- Individual participant data will not be publicly disclosed.
- The study protocol and summary results may be registered on a public clinical trial registry (e.g., ClinicalTrials.gov or Indonesian equivalent) if required by journal policies.

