Intervention: Both groups receive nutritional education. Participants in the intervention group will receive a structured chair-based exercise program followed by guided intergenerational activities designed to enhance physical capacity, cognitive stimulation, and social engagement. The control group will receive usual care. Intervention group: 12 weeks structured chair-exercise (PEROSI protocol, progressive frequency 1-3x/week, 60 min/session) followed by 4 weeks SHP (8 sessions, 2x/week, 45 min, paired elderly-child activities using AMIR materials). The control group will receive education only.

Main study parameters/endpoints: The primary outcomes include changes in physical performance and cognitive function. Secondary outcomes include changes in frailty status, quality of life, and psychosocial well-being.

Nature and extent of the burden and risks associated with participation, benefit, and group relatedness: Participation in this study involves minimal to low risk. The primary potential risks are related to the structured chair-based exercise, including mild musculoskeletal discomfort, transient fatigue, muscle soreness, dizziness, or shortness of breath, particularly during the initial sessions. These risks are considered low and are commonly associated with light-to-moderate physical activity in older adults. To minimize these risks, all exercise sessions will be conducted under supervision by trained personnel, with prior health screening and continuous monitoring of participants' physical condition.

Intergenerational activities are non-invasive and pose no physical risk; however, minor psychological discomfort, such as temporary feelings of anxiety or social unease, may occur during initial interactions. These activities will be conducted in a supportive and controlled environment to ensure participants' comfort and emotional safety.

The overall burden to participants includes time commitment for attending intervention sessions and undergoing physical, cognitive, and laboratory assessments. Blood sampling for laboratory analysis may cause mild pain, bruising, or discomfort at the puncture site, with no expected long-term adverse effects.

Potential benefits for participants include improvement in physical function, cognitive performance, frailty status, social engagement, and overall quality of life. The anticipated benefits are considered to outweigh the minimal risks associated with study participation.

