2. OBJECTIVES

Primary Objectives

To evaluate the effects of 12 weeks of structured physical exercise (chair-based PEROSI protocol) followed by 4 weeks of social heterochronic parabiosis (SHP)-based intergenerational

intervention on frailty syndrome and serum mature brain-derived neurotrophic factor (mBDNF) levels in community-dwelling elderly with physio-cognitive decline syndrome (PCDS).

Secondary objectives

- To analyze the effects of the combined intervention over 16 weeks on hand grip strength in elderly with PCDS.
- To analyze the effects of the combined intervention over 16 weeks on gait speed in elderly with PCDS.
- To analyze the effects of the combined intervention over 16 weeks on cognitive function as measured by the MoCA-Ina score in the elderly with PCDS.
- To evaluate the effects of the combined intervention over 16 weeks on health-related quality of life in the elderly with PCDS.
- To assess correlations between changes in serum mBDNF levels and changes in MoCA-Ina score, hand grip strength, and gait speed in the elderly with PCDS.

Hypothesis

Elderly people with physio-cognitive decline syndrome (PCDS) who receive 12 weeks of structured physical exercise followed by 4 weeks of social heterochronic parabiosis (SHP)-based intergenerational intervention on top of nutritional education have significantly better frailty syndrome status and higher serum mature brain-derived neurotrophic factor (mBDNF) levels than those receiving nutritional education alone after 16 weeks of intervention, along with greater improvements in hand grip strength, gait speed, cognitive function (MoCA-Ina score), and health-related quality of life.

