7. METHODS

7.1 Study parameters/endpoints

7.1.1 Main study parameter/endpoint

- Change in frailty syndrome status (assessed using Cardiovascular Health Study criteria: score 0 robust, 1–2 pre-frail, ≥3 frail) from baseline to week 16.
- Change in serum mature brain-derived neurotrophic factor (mBDNF) levels (measured by ELISA) from baseline to week 16.

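### Section 11.6 leaves registration optional, undated and tied to journal policy, so the protocol does not ensure a public dated record of a primary endpoint that it states in two ways

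*Combined protocol and SAP*

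**What the plan says.** On registration, section 11.6 states that the protocol and summary results "may be registered on a public clinical trial registry (e.g., ClinicalTrials.gov or Indonesian equivalent) if required by journal policies". It gives no timing, registry identifier or target journal. The same section promises that "Results will be published in peer-reviewed scientific journals" and that "Authorship will follow International Committee of Medical Journal Editors (ICMJE) guidelines"; the ICMJE reference is attached to authorship, not to registration. No other section expressly commits to registering the trial.

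On the primary endpoint, the Summary says "The primary outcomes include changes in physical performance and cognitive function" and then "Secondary outcomes include changes in frailty status, quality of life, and psychosocial well-being". Section 2 gives as the primary objective the effect of the "intervention on frailty syndrome and serum mature brain-derived neurotrophic factor (mBDNF) levels in community-dwelling elderly" with PCDS. Section 7.1.1 lists two main endpoints: "Change in frailty syndrome status (assessed using Cardiovascular Health Study criteria: score 0 robust, 1–2 pre-frail, ≥3 frail) from baseline to week 16" and "Change in serum mature brain-derived neurotrophic factor (mBDNF) levels (measured by ELISA) from baseline to week 16". Section 7.1.2 places grip strength, gait speed, MoCA-Ina and SF-12 among the secondary endpoints.

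On other records, section 10 requires written ethics approval before the study starts, and section 11.3 requires ethics approval before any substantial amendment takes effect.

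**The concern.** Prospective registration lets a reader of the eventual paper check that the outcome reported as primary was the one chosen beforehand. A rule that depends on a journal's policy can be met late, because the plan does not say when the journal is chosen or its policy consulted. In many trials the protocol itself would fill the gap. Here it cannot, because a paper could cite the Summary for one primary set and section 7.1.1 for another, each in good faith.

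The design adds some weight. Section 7.2 describes an open-label trial in which the research team cannot be blinded (section 5 says the opposite about investigators, which also needs reconciling). Section 9 tests at p<0.05 with no rule for multiple outcomes. What is at stake is whether the headline result can be read as confirmatory.

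**Working it through.** **The plan's own figure.** The registration clause contains none. The sample size does reproduce: the largest requirement is 42 per group (section 4.5) and the drop-out allowance is 15% (section 7.6), so 42/(1 − 0.15) = 49.4, rounded up to 50 per group. Registration does not change it.

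**The passages side by side.**

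| Place | Physical performance | Cognition | Frailty | mBDNF | Quality of life |
|---|---|---|---|---|---|
| Summary | primary | primary | secondary | not listed | secondary |
| Section 2, objectives | secondary (grip, gait speed) | secondary | primary | primary | secondary |
| Sections 7.1.1 and 7.1.2 | secondary (grip, gait speed) | secondary | primary | primary | secondary |
| Section 4.5, sample size | listed, no rank | listed, no rank | absent | listed, no rank | listed, no rank |
| Section 9, analysis | listed, no rank | listed, no rank | absent | listed, no rank | listed, no rank |

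The Summary stands alone against sections 2 and 7.1.1. Sections 4.5 and 9 do not settle the matter, since neither singles out a primary outcome and both omit one of the two main endpoints of 7.1.1.

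**Illustrative size.** The inputs are 0.05 per test with no multiplicity rule (section 9). The Summary does not define physical performance; I read it as grip strength and gait speed, the two physical measures in 7.1.2. Success is taken as any one endpoint reaching p<0.05, because the plan does not say whether one or all must. With no true effect and k independent tests, the chance of at least one false p<0.05 is 1 − 0.95^k.

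- Section 7.1.1 set (frailty, mBDNF), k = 2: 1 − 0.9025 = 9.75%.
- Summary set (grip, gait speed, MoCA-Ina), k = 3: 1 − 0.8574 = 14.3%.
- Free choice between the two sets, k = 5: 1 − 0.7738 = 22.6%.

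Independence does not hold here. The CHS frailty criteria in section 7.3.4 include grip weakness and gait slowness, so frailty overlaps with two of the other four outcomes. Positive correlation pulls each figure down towards 5%. The true values cannot be computed because the documents give no correlations.

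**The case against.** The strongest reply is that controls already exist. The protocol goes to an ethics committee, the study cannot begin without written approval, and changes touching scientific integrity need approval first. That is a real and dated constraint. It is not public, however, and the approved text carries both versions of the primary endpoint, so it cannot show which was chosen.

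Second, the two versions are not of equal standing. The introduction, the primary objective, the lead hypothesis and section 7.1.1 all name frailty and mBDNF; only the Summary differs. This stands. It makes 7.1.1 the natural version to keep, but it does not remove the conflict.

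Third, the clause might itself lead to timely registration, if a journal requiring it is chosen early. That is possible, but the clause does not secure it.

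Fourth, one of the two main endpoints is protected at measurement: mBDNF is assayed in an accredited laboratory by analysts blinded to allocation (sections 7.2 and 7.3.3). The point about an unblinded team therefore does not extend to that measurement. The lack of a safety board and of external monitoring (sections 8.5 and 11.2) is explained by low risk and says little about outcome switching.

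A reader might also infer that section 11.6 breaks its own promise of transparent dissemination. It does not: journal publication of results is promised without condition.

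**Conclusion.** The concern holds in a limited form. The protocol does not commit to prospective registration, and so does not ensure a public dated record of the primary endpoint, in a plan whose sections disagree on what that endpoint is. The endpoint conflict is the weightier defect; registering the present text would only publish it.

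A reader might infer that the trial is unregistered or that no public record exists. The documents cannot show this: they contain no registry record, and the front pages were not in the text available for review. Nor do they suggest any intention to switch outcomes.

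A reader might also count six outcomes, adding quality of life, for 1 − 0.95^6 = 26.5%, and compare that with 5%. Neither figure is apt. Quality of life is secondary in both the Summary and 7.1.2, so five outcomes is the right count. The comparator after the fix is two endpoints, not one. The fair illustration is about 23% against about 9.8%. Both assume independence, no true effect, and success on any one endpoint, and both are lower with positive correlation. Registration does not deal with the remaining 9.8%; that is a multiplicity question for section 9.

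**What to change.** 1. Align the Summary with section 7.1.1 and add the between-group frailty comparison to section 9, so that one primary set at week 16 is stated throughout. Section 4.5 should identify the same set.
2. Replace the sentence in section 11.6 with a commitment to register the trial on a public registry before the first participant is enrolled, with those endpoints and the week-16 time point, to record and date any later change there, and to post summary results whatever the journal.
3. If the trial is already registered, cite the identifier and date in section 11.6. If enrolment has begun without registration, register before any comparison by arm and state the date.

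The order matters, because step 2 protects nothing until step 1 is done. The cost is a few edited sentences, a registry entry and, if the protocol is already approved, submission of the endpoint change to the ethics committee under section 11.3. No study procedure changes, and registration itself leaves the sample size of 100 as it is.

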12. STRUCTURED RISK ANALYSIS

12.1 Potential issues of concern

The study involves minimal-risk non-pharmacological interventions in vulnerable populations (elderly with physio-cognitive decline syndrome and young children from orphanages). Potential concerns include:

- Physical risks to elderly participants: Mild fatigue, muscle soreness, minor strain, or low risk of fall during supervised chair-based exercise; minor bruising or discomfort from venipuncture (three blood draws).
- Psychological/emotional risks: Initial anxiety, awkwardness, or discomfort during intergenerational interactions for both elderly (interacting with unfamiliar children) and children (interacting with elderly with physical/cognitive limitations); potential transient emotional distress if interactions are not harmonious.
- Logistical/operational risks: Transportation issues to/from orphanages; adherence challenges due to elderly mobility or motivation; potential loss to follow-up in community setting; coordination difficulties with multiple orphanages.
- Data and confidentiality risks: Unintentional breach of personal data during digital transfer (e-fliers, tele-conferences) or storage.
- Equity and coercion risks: Perception of undue influence on orphanage children or elderly due to incentives (snacks, transport reimbursement, stationery).

- Unforeseen risks: Acute unrelated illness in elderly triggering withdrawal; seasonal factors (e.g., weather, holidays) affecting session attendance.

12.2 Synthesis

This structured risk analysis concludes that the overall risk level is minimal and acceptable given the study's objectives and population. The interventions (PEROSI chair-exercise and AMIR-based intergenerational activities) are established, low-intensity, community-based practices with proven safety profiles in similar geriatric and intergenerational programs.

All identified risks are effectively mitigated through: rigorous screening/exclusion criteria; progressive/supervised exercise with termination guidelines; professional blood sampling; preparatory training (ToT) and on-site supervision for intergenerational sessions; child-friendly approaches and orphanage oversight; proactive adherence support (phone counseling, transport provision); secure data handling; and voluntary participation with clear withdrawal rights.

Potential benefits (improved physical/cognitive function, reduced frailty and isolation, enhanced neuroplasticity via mBDNF, intergenerational empathy, and healthy lifestyle education) substantially outweigh the minimal risks for both elderly and child participants. The control group receives meaningful nutritional education and monitoring, ensuring ethical equipoise. No serious intervention-related harm is anticipated; any adverse events will be promptly managed and reported. The benefit-risk balance strongly supports proceeding with the study under close internal oversight and Ethics Committee approval.

